#### **7.4 Interim Analyses and Data Monitoring**

To meet the trial's ethical responsibility to its subjects, results will be monitored by two independent groups that have no formal involvement with the subjects or the investigation, as follows:

1. DSMB – Data Safety Monitoring Board
2. CEC – Clinical Events Committee

The members of these committees shall function independently of HeartWare and the CRO.

The DSMB will review the study at key points during the conduct. Details of the DSMB safety review meetings will be detailed in a separate DMC Charter.

#### **7.5 Multi-center Studies and Pooling of Centers**

Patients will be pooled across sites for analysis of study endpoints.

Site effects will be performed for the primary endpoint using site as a blocking variable. Sites with at least 8 patients will retain their identities. Smaller sites will be ranked in decreasing order of size and cumulatively pooled until pooled sites of no less than 8 are achieved.

#### **7.6 Multiple Comparisons/Multiplicity**

No adjustments for multiple comparisons or multiplicity will be made.

The family wise error rate has not been affected by multiplicity for two reasons: the distinction between primary and secondary for the hypothesized endpoints, and the expected correlation between the hypothesized endpoints.

Adjustments to the significance level are not necessary; however careful consideration will be used when making statements concerning the first secondary endpoint.

### **7.7 Use of an “Efficacy Subset” of Patients**

Not applicable to this study.

### **7.8 Active-Control Studies Intended to Show Equivalence**

Not applicable to this study.

### **7.9 Examination of Subgroups**

No examination of the primary or secondary efficacy variable by subgroups is planned.

## **8 STATISTICAL ANALYSIS**

### **8.1 Disposition of Patients**

The number of patients enrolled, who received an implant, and who are evaluable will be summarized. The number of treated patients who completed the study, the number of patients who discontinued from the study and the reasons for discontinuing from the study will also be summarized. Patients who died prior to 24 months are considered achieving the endpoint and therefore they would be included in the ‘completed the study’ category.

### **8.2 Protocol Deviations**

Important protocol deviations (IPDs) will be summarized. The HeartWare review team will identify IPD categories. The IPD specifications will be defined prior to the close of the database for the interim analysis. An overall IPD listing will be reviewed just prior to database closure for the interim analysis and database lock for final analysis. The HeartWare review team will approve all final IPD determinations. The HeartWare review team will consist of the clinical monitoring manager, clinical project manager, data manager, biostatistician, and regulatory representative. Once all IPD determinations are finalized and approved by the HeartWare review team, the database will be closed for statistical analysis. The number of patients in each IPD category will be summarized. All IPDs will be listed by patient.

### **8.3 Analysis Populations**

### **8.3.1 Enrolled Population**

All patients who signed informed consent will be included in this analysis set. This analysis set will be used only for patient accountability for disposition purposes.

### **8.3.2 Intent-to-Treat (ITT) Population**

All patients who enroll in the study (i.e., have signed informed consent) and who undergo anesthesia for implantation will be included in this analysis set. This population will be the primary analysis population.

### **8.3.3 Per Protocol (PP) Population**

Patients in the ITT Population who received HeartWare MVAD® will form the Per Protocol (PP) Population.

Efficacy analysis will be conducted for both ITT and PP analysis sets, differences in results using the two analyses will be carefully examined.

### **8.3.4 Safety Population**

Patients in the ITT Population who received HeartWare MVAD® will form the Safety Population. This population will be used in all safety reporting and analysis.

## **8.4 Demographic and Other Baseline Characteristics**

Demographic and baseline characteristics will be summarized for ITT and PP populations.

Gender, race, and ethnicity will be summarized using counts and percentages. Age (years), height (cm), weight (kg), body surface area [BSA (m^2)], body mass index (BMI) (kg/m^2) will be summarized with descriptive statistics.

The number and percentage of patients with medical history events will be summarized. Cardiovascular history at baseline and comorbidities at baseline will be summarized separately. Vital signs collected at screening will be summarized with descriptive statistics. Smoking status will be summarized using counts and percentages.

The following implant data will be summarized.

1. Cardiopulmonary bypass (yes/no)
2. Total time on bypass
3. Surgical technique (sternotomy, thoracotomy, other)
4. Outflow graft location (ascending aorta, descending aorta, subclavian, other)
5. Any concomitant cardiac procedure (yes/no)
6. Intraventricular thrombus (none, present, not assessed, not applicable)

7. Transfusion in operating room (yes/no)
8. Driveline location (right upper quadrant, right lower quadrant, left upper quadrant, left lower quadrant)

The following discharge parameters will be summarized.

1. Discharge to (home, skilled nursing care facility, inpatient rehabilitation facility, hospice, other)
2. Days in ICU
3. Days in general ward

## 8.5 MVAD® Parameters

LVAD, including flow, speed, and power, will be tabulated by time point with descriptive statistics. This summary will be performed for PP population.

## 8.6 Prior and Concomitant Therapy

The World Health Organization (WHO) Drug Dictionary (version 16.0) will be used to classify medications by preferred term and WHO Anatomical Therapeutic Chemical (ATC) classification of ingredients.

Medications will be summarized using counts and percentages by WHO ATC classification of ingredients and by preferred term. This summary will be performed for ITT population.

Medications with start date and stop date prior to implant will be included in the prior medication summary. Medications taken during the study, including those started prior to implant, will be included in the concomitant medication summary.

## 8.7 Analysis of Efficacy Parameters

All primary and secondary efficacy analyses will be performed on ITT and PP populations.

### 8.7.1 Analysis of Primary Efficacy Variable – Overall Survival at 6 Months

The primary endpoint is survival at 6 months presented as a simple proportion (subjects alive on the MVAD® pump divided by endpoint eligible subjects). Transplants, explants for recovery and exchanges (to a device other than the MVAD® Pump) prior to 6 month follow-up will be eligible for endpoint analysis (with survival status identified at the time of the procedure). Trial failure is associated with events (death) on the MVAD® Pump. The survival incidence at 6 months is estimated to be 85%, based on HeartWare's experience with the HVAD. This estimate will be compared to a performance goal (PG1). The null and alternative hypotheses are provided below:

$$H_0: \pi_{MVAD1} \leq PG_1$$

$$H_A: \pi_{MVAD1} > PG_1$$

$\pi_{MVAD1}$  is the estimated proportion of survival in the treatment group. The performance goal at 6 months is 70%. Success is achieved if the lower bound of the one-sided 95% exact binomial confidence interval exceeds the performance goal.

A summary table will include number of patients alive and number of patients dead by study day 183 (the lower bound of the 6 month visit), the proportion for overall survival at 6 months, and the associated lower and the upper 90% exact binominal confidence intervals.

Sensitivity analysis will be performed to assess the impact of the missing data (See Section 8.7.5.1).

### ***8.7.2 Analysis of Secondary Efficacy Variable – Overall Survival at 24 Months***

The first secondary endpoint is survival at 24 months presented as a simple proportion (defined like the primary endpoint). The survival incidence at 24 months is estimated to be 70%, based on HeartWare's experience with the HVAD. This estimate will be compared to a performance goal (PG2). The null and alternative hypotheses are provided below:

$$H_0: \pi_{MVAD2} \leq PG_2$$

$$H_A: \pi_{MVAD2} > PG_2$$

$\pi_{MVAD2}$  is the estimated proportion of survival in the treatment group. The performance goal at 24 months is 52.5%. Success is achieved if the lower bound of the one-sided 95% exact binomial confidence interval exceeds the performance goal.

A summary table will include the number of patients alive and number of patients dead by study day 730 (the lower bound of the 24 month visit), proportion of overall survival at 24 months and the associated lower and the upper 90% exact binominal confidence intervals.

### ***8.7.3 Analysis of Other Secondary Efficacy Variables***

Analysis for overall survival (TTD), health status (KCCQ, EuroQoL EQ-5D-5L), and functional status (NYHA, 6 minute walk) will be performed on both the ITT and PP populations. Analysis for NIHSS and MRS will be performed on both the ITT and PP populations.

#### ***8.7.3.1 Overall Survival (TTD)***

TTD will be derived from the Kaplan-Meier estimates and 95% confidence intervals will be calculated. The quartiles for Kaplan-Meier estimates will all be presented. Plot of the Kaplan-Meier curve will be provided. This analysis will be performed on both the ITT and PP populations.

#### 8.7.3.2 *Kansas City Cardiomyopathy Questionnaire (KCCQ)*

KCCQ scale scores and change from baseline will be summarized by each scheduled visit using descriptive statistics, including 95% CI for the mean. Only patients that are currently on device at the given time point will be summarized.

#### 8.7.3.3 *EuroQol-5D-5L*

The health status data will be tabulated by scheduled time point for each dimension and health profile with number and percentage in each category.

EQ VAS data and the change from baseline will be tabulated by scheduled time point using descriptive statistics, including the 95% CI for the mean. The EQ index value and the change from baseline will be tabulated by time point using descriptive statistics of sample size (N), mean, 95% CI for the mean, minimum, maximum, median, and standard deviations. Only patients that are currently on device at the given time point will be summarized.

#### 8.7.3.4 *6-Minute Walk*

Results of the 6-minute walk at each scheduled visit and change from baseline to visit will be tabulated by time point using descriptive statistics, including 95% confidence intervals for the means.

#### 8.7.3.5 *NYHA Classification*

Results of the NYHA classification at screening (baseline) and each scheduled post implant follow-up visits will be tabulated. Change from baseline in NYHA classification will also be summarized in a shift table.

#### 8.7.3.6 *NIH Stroke Scale*

Results of the total raw NIHSS score at each visit and change from baseline to visit will be tabulated by scheduled time point using descriptive statistics, including 95% confidence intervals for the means. A table of change from stroke values to 12 weeks post-stroke and of change from stroke to 24 weeks post-stroke will be presented using descriptive statistics, including 95% confidence intervals for the means.

#### 8.7.3.7 *Modified Rankin Scale*

Results of the MRS by category (MRS Score of 0, 1, 2, 3, 4, 5, and 6) at each scheduled visit will be tabulated using counts and percentages. A shift table of change from stroke to 12 weeks post-stroke and of change from stroke to 24 weeks post-stroke will be presented using counts and percentages.

### **8.7.4 Subgroup Analyses**

No subgroup analyses of efficacy data are planned.

### **8.7.5 Exploratory Analyses**

#### *8.7.5.1 Sensitivity Analysis*

If there are any patients implanted with MVAD® for whom the primary efficacy endpoint cannot be assessed, then a sensitivity analysis will be conducted, where patients with missing outcomes will be imputed as failures (death).

A simple proportion of overall survival at 6 months and exact binomial confidence intervals will be computed as described in the Analysis of Primary Efficacy Variable (Section 8.7.1).

## **8.8 Analysis of Safety**

All safety analyses will be performed using the safety population. Formal inferential statistics will not be conducted.

### **8.8.1 Extent of Exposure and Compliance to Study Treatment**

No formal tabulations are planned since all qualified patients will have received MVAD® system in the hospital.

### **8.8.2 Adverse Events**

#### *8.8.2.1 Adverse Events based on INTERMACS definition*

The number and percentage of patients experiencing each specified AE using the INTERMACS definition will be summarized. Any AEs that are not treatment emergent will be listed only.

The incidence of AEs using the INTERMACS definition will be reported in the categories of bleeding (re-hospitalization, re-operation, gastrointestinal (GI)), cardiac arrhythmia (ventricular, supraventricular), device malfunction/failure, hemolysis, hepatic dysfunction, hypertension, infection (localized non-device, sepsis, driveline exit site), myocardial infarction, neurological dysfunction (CT confirmed ischemic cerebral vascular accident (CVA), CT confirmed hemorrhagic CVA, transient ischemic attack (TIA)), pericardial fluid collection, psychiatric episode, renal dysfunction (acute, chronic), respiratory dysfunction, right heart failure, arterial non-CNS thromboembolism, venous thromboembolism, wound dehiscence, and other event. In addition to the incidence rate, the number of events and the

event rate per patient year will be reported for each INTERMACS-defined adverse event. For the incidence rate, a patient will only be counted once per each INTERMACS-defined category and counted once per each INTERMACS-defined sub-category. The following summaries will be presented.

1. All Treatment Emergent Site-Reported AEs by INTERMACS-defined term
2. All Treatment Emergent Site-Reported ADEs by INTERMACS-defined term
3. All Treatment Emergent Site-Reported Non-ADEs by INTERMACS-defined term
4. All Treatment Emergent Site-Reported ADEs by INTERMACS-defined term – Related to MVAD System
5. All Treatment Emergent Site-Reported Serious AEs by INTERMACS-defined term
6. All Treatment Emergent Site-Reported Serious ADEs by INTERMACS-defined term
7. All Treatment Emergent Site-Reported Serious non-ADEs by INTERMACS defined term
8. All Treatment Emergent Site-Reported Serious ADEs by INTERMACS-defined term – Related to MVAD System
9. All Treatment Emergent Site-Reported AEs leading to outcome of fatal by INTERMACS-defined term
10. All Treatment Emergent Site-Reported AEs leading to exchange/explant of device by INTERMACS-defined term
11. All Treatment Emergent Adjudicated AEs by INTERMACS-defined term
12. All Treatment Emergent Adjudicated ADEs by INTERMACS-defined term
13. All Treatment Emergent Adjudicated Non-ADEs by INTERMACS-defined term
14. All Treatment Emergent Adjudicated ADEs by INTERMACS-defined term – Related to MVAD System
15. All Treatment Emergent Adjudicated Serious AEs by INTERMACS-defined term
16. All Treatment Emergent Adjudicated Serious ADEs by INTERMACS-defined term
17. All Treatment Emergent Adjudicated Serious non-ADEs by INTERMACS defined term
18. All Treatment Emergent Adjudicated Serious ADEs by INTERMACS-defined term – Related to MVAD System
19. All Treatment Emergent Adjudicated AEs leading to outcome of fatal by INTERMACS-defined term
20. All Treatment Emergent Adjudicated AEs leading to exchange/explant of device by INTERMACS-defined term

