#### 6.4 Secondary Endpoints

1. Survival at 24 months presented as a simple proportion (defined like the primary endpoint)
2. Overall Survival (Time to Death)
3. Incidence of major bleeding, per INTERMACS definition
4. Incidence of all device failures and device malfunctions per INTERMACS definition
5. Incidence of major infection, per INTERMACS definition
6. Incidence of neurological dysfunction per INTERMACS definition
7. Health Status change, as measured by Kansas City Cardiomyopathy Questionnaire (KCCQ) and EuroQol EQ-5D-5L
8. Functional status change, as measured by NYHA and 6-minute walk
9. Frequency and rates of adverse events(AEs) throughout VAD support per INTERMACS Definition
10. Length of operative time and initial hospital stay
11. Re-Hospitalizations(excluding planned procedures)
12. Transplantations
13. Explants

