**DEVICE MALFUNCTION:**

A **Device Malfunction** occurs when any component of the MCSD system ceases to operate to its designed performance specifications or otherwise fails to perform as intended. Performance specifications include all claims made in the Instructions for Use.

Device malfunctions can be further defined as **major** or **minor**:

1. **Major device malfunction**, otherwise known as failure, occurs when one or more of the components of the MCSD system either directly causes or could potentially induce a state of inadequate circulatory support (low cardiac output state) or death. A failure that was iatrogenic or recipient-induced will be classified as an Iatrogenic/Recipient-Induced Failure. A device malfunction or failure is considered major when one of the following conditions occurs:
  - a. Suspected or confirmed pump thrombus (see below)
  - b. Urgent transplantation (immediate 1A listing for transplant)
  - c. Pump replacement
  - d. Pump explant
  - e. Breach of integrity of drive line that required repair
  - f. Death
2. **Minor device malfunction** includes inadequately functioning external components which require repair or replacement but do not result in 1a-f. Device malfunction does not apply to routine maintenance which includes repair/replacement of: external controller, pneumatic drive unit, electric power supplies, batteries and interconnecting cables.

**Pump Thrombus** represents a special case of major device malfunction and can be delineated as **suspected pump thrombus** or **confirmed pump thrombus**. Pump thrombus will be classified as **SUSPECTED** (see definition below) based upon clinical, biochemical, or hemodynamic findings or **CONFIRMED** (see definition below) based upon device inspection or incontrovertible radiologic studies or absence of appropriate Doppler flow signals that confirms thrombus within the device or its conduits that results in or could potentially induce circulatory failure.

1. **Suspected pump thrombus** is a pump-related malfunction in which clinical or MCSD parameters suggest thrombus on the blood contacting components of the pump, cannulae, or grafts. Signs and symptoms should include at least 2 of the 3 following criteria:
  - a. **Presence of hemolysis**
  - b. **Presence of heart failure not explained by structural heart disease**
  - c. **Abnormal pump parameters**

Suspected pump thrombus should be accompanied by 1 or more of the following events or interventions:

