#### **Internal Pump Component, Inflow or Outflow Tract Infection**

Infection of blood-contacting surfaces of the LVAD documented by positive site culture. (There should be a separate data field for paracorporeal pump that describes infection at the percutaneous cannula site, e.g. Thoratec PVAD).

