**NEUROLOGICAL DYSFUNCTION:**

Any new, temporary or permanent, focal or global neurologic dysfunction ascertained by a standard neurological history and examination administered by a neurologist or other qualified physician and documented with appropriate diagnostic tests and consultation note; or an abnormality identified by surveillance neuroimaging. The examining physician will classify the event as a cerebrovascular event as defined below or as a non-vascular acute neurologic event. A neurologic event may be recognized by a clinically evident sign or symptom, or by clinically-silent electrographic seizure activity, or as a clinically silent lesion detected by surveillance neuroimaging. Each neurologic event should be classified by the clinical provider following complete neurologic assessment as one of the following event types:

- a. Transient ischemic attack, defined as an acute transient neurologic deficit conforming anatomically to arterial distribution cerebral ischemia, which resolves in < 24 hours and is associated with no infarction on brain imaging (head CT performed >24 hours after symptom onset; or MRI\*).
- b. Ischemic stroke, defined as a new acute neurologic deficit (or acute encephalopathy or seizures in children <6 months\*\*) of any duration associated with acute infarction on imaging corresponding anatomically to the clinical deficit. Ischemic stroke should be sub classified as due to arterial-distribution ischemia or due to venous thrombosis.
- c. Acute symptomatic intracranial hemorrhage, defined as new acute neurologic deficit (or acute encephalopathy or seizures in children < 6 months\*\*) attributable to Intracranial hemorrhage (ICH). ICH subtype should be specified as one or a combination of the following types: subarachnoid, intraventricular, parenchymal, subdural.
- d. Clinically covert ischemic stroke or ICH: infarction or ICH seen by surveillance imaging, without clinical findings of stroke or ICH at the time of event recognition.
- e. Hypoxic-Ischemic Encephalopathy: Acute new encephalopathy\*\*\* due to hypoxic-ischemic injury (HIE), manifest as clinically- evident signs or symptoms, or subclinical electrographic seizures found by complete neurological diagnostic evaluation to be attributable to acute global or focal hypoxic or ischemic brain injury not meeting one of ischemic stroke or ICH events as defined above.

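### The adverse event sub-categories in SAP 8.8.2.1 conflict with protocol Appendix 17.9: one infection category and three neurological types are missing, strokes need CT confirmation, and pump thrombus is pooled with other malfunctions

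*SAP*

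**What the plan says.** Protocol 6.4 ties secondary endpoints 3 to 6 (major bleeding, device failures and malfunctions, major infection, neurological dysfunction) to the INTERMACS definitions. The fourth reads "Incidence of all device failures and device malfunctions per INTERMACS definition". Protocol 10.3.1.1 has events classified under those definitions, and protocol 16.2.3 has the clinical events committee adjudicate with them. SAP 6.6.2 names Appendix 17.9 as the place where they are set out.

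Appendix 17.9 divides device malfunction into major (also called failure) and minor. Pump thrombus "represents a special case of major device malfunction and can be delineated as" suspected or confirmed. One of the infection categories is "Infection of blood-contacting surfaces of the LVAD documented by positive site culture". Each neurological event is to be assigned to one of six types, the fourth being "Clinically covert ischemic stroke or ICH: infarction or ICH seen by surveillance imaging".

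SAP 8.8.2.1 gives device malfunction/failure as a single category and, further on, "infection (localized non-device, sepsis, driveline exit site), myocardial infarction, neurological dysfunction (CT confirmed ischemic cerebral vascular accident (CVA), CT confirmed hemorrhagic CVA", with TIA as the third neurological type. Its counting rule is that "a patient will only be counted once per each INTERMACS-defined category and counted once per each INTERMACS-defined sub-category".

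SAP 5.2, as it stands in version 2.0, reports that enrolment stopped below 15 subjects and that individual case studies replace summary statistics. Section 8.8.2.1 still says that its summaries will be presented, and SAP 8.8.2.2 still plans patient listings for each INTERMACS definition.

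**The concern.** The SAP points to one set of definitions and tabulates another. Because patients are counted once per category and once per sub-category, the sub-category list decides which types of event a reader can see.

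Two kinds of fault follow. The first is omission: an event that 17.9 requires to be typed has no place in the SAP list under that type. The second is an added condition: a stroke that satisfies 17.9 fails the SAP's sub-row if the imaging was not CT.

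This is the first clinical use of the pump (protocol 4.1). Thrombus and infection on the blood-contacting surfaces, and covert or hypoxic brain injury, are among the event types a reader would look for. The protocol expects thrombosis often enough to give it an anticipated rate of its own, and the pooled SAP row can be compared neither with that rate nor with the separate rate for device malfunction.

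**Working it through.** **Side-by-side comparison**

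| Item | Protocol Appendix 17.9 | SAP 8.8.2.1 | Missing or changed |
|---|---|---|---|
| Infection | 4 categories: localized non-device; percutaneous site/pocket; internal pump, inflow or outflow; sepsis | 3: localized non-device; sepsis; driveline exit site | Internal pump, inflow or outflow |
| Neurological dysfunction | 6 types: TIA; ischemic stroke; symptomatic intracranial hemorrhage; covert stroke or hemorrhage; hypoxic-ischemic encephalopathy; other acute encephalopathy | 3: ischemic CVA; hemorrhagic CVA; TIA | Covert stroke or hemorrhage; hypoxic-ischemic; other encephalopathy |
| Evidence for stroke | Ischemic: infarction on imaging, method not named. Hemorrhage: new deficit attributable to it, no CT condition | CT confirmation for both | Condition added |
| Device malfunction | Major and minor; suspected and confirmed pump thrombus within major | One undivided row | All splits |

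The driveline exit site row is taken as the SAP's counterpart of the percutaneous site/pocket category.

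**How many thromboses would be pooled**

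The plan gives no figure to reproduce here. The inputs are:

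- anticipated device thrombosis, 0.1 per patient-year (protocol 10.1.4.1; device malfunction has its own line at below 0.05);
- 60 subjects, with survival of 85% at 6 months and 70% at 24 months (protocol 12.3 and 12.4);
- fewer than 15 enrolled, so at most 14 (SAP 5.2).

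Assumptions: survival falls linearly between these points, and there are no transplants, explants or losses.

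Patient-years per subject = 0.5 × (1 + 0.85)/2 + 1.5 × (0.85 + 0.70)/2 = 0.4625 + 1.1625 = 1.625.

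- Planned size: 60 × 1.625 = 97.5 patient-years; 97.5 × 0.1 = 9.75, about 10 events.
- Enrolled, same survival: 14 × 1.625 = 22.75 patient-years; × 0.1 = about 2.3 events.
- Enrolled, everyone followed for two years: 14 × 2 = 28 patient-years; × 0.1 = 2.8 events.

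The documents do not give the follow-up actually achieved. Shorter follow-up lowers the last two figures.

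**The case against.** The strongest reply is that nothing the endpoints ask for is lost. Each of endpoints 3 to 6 has a parent category in 8.8.2.1, and endpoint 4 covers all failures and malfunctions, so the pooled row is that endpoint as worded. This stands. A reader might infer that the endpoints cannot be computed; the documents do not support that.

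A reader might also infer that a thrombosed pump cannot be told apart from a minor external fault. That goes too far. Summaries 5 to 8 and 15 to 18 separate serious events, 9 and 19 fatal ones, and 10 and 20 those leading to exchange or explant. Appendix 17.9 also excludes routine repair or replacement of controllers, batteries and cables from malfunction. What remains is narrower: a suspected thrombus that ends in neither death nor removal of the pump is not separable from other malfunctions of the same seriousness.

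Nor do overall stroke-related counts turn on the scanner. A stroke shown only by MRI is still adjudicated under the INTERMACS definition and still counts as neurological dysfunction; only its sub-row is affected. In 17.9, MRI is named only under TIA, but ischemic stroke there rests on imaging in general.

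It can be argued that the SAP list is illustrative, since 8.8.2.1 also refers to INTERMACS-defined sub-categories and terms. This makes the omissions partly an ambiguity. It does not remove the CT condition, which is a stated restriction, and a programmer would build the tables from the list as written.

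Finally, SAP 5.2 drops the summaries. That reduces the practical effect considerably, and the figure of about 10 thromboses does not describe the trial as it ended. But 8.8.2.1 was not brought into line with 5.2, and the listings and case studies still need headings.

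**Conclusion.** The mismatch is confirmed on the text: one of four infection categories and three of six neurological types have no sub-row, both stroke sub-rows carry a CT condition absent from 17.9, and pump thrombus has no row of its own. The effect is confined to sub-types. The primary endpoint is untouched and the parent incidences are intact.

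The size for thrombosis rests on the protocol's anticipated rate holding for this pump and on the survival and follow-up assumptions above. It is about 10 pooled events as designed, and at most about 2 to 3 as enrolled. No comparable figure can be given for the missing infection and neurological types, because the anticipated rates in protocol 10.1.4.1 are not broken down that way.

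Appendix 17.9 also separates minor from major hemolysis, grades right heart failure and lists several criteria for major bleeding. A reader might infer that the SAP must tabulate each of these. No endpoint requires those splits, so they are optional. The point merits correction because part of the plan is wrong as written and the remedy is cheap.

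**What to change.** In SAP 8.8.2.1:

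- delete the CT condition from both stroke sub-rows;
- list all four infection categories and all six neurological types of Appendix 17.9;
- divide device malfunction into major and minor, with suspected and confirmed pump thrombus shown within major.

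Use the same headings in the listings by INTERMACS definition (SAP 8.8.2.2) and in the case studies, and state in 8.8.2.1 which of its summaries survive SAP 5.2. With so few subjects, the case studies and listings are where the event type will actually be read.

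The cost is SAP wording and display shells. Classification and committee adjudication under these definitions are already required, including reclassification of a suspected thrombus once it is confirmed. The case report forms are not among the documents, so the sponsor should check that each sub-type is captured as a field.
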